4.2.2 Analysis of Secondary Effectiveness Variable

The UF rate, UF volume, and treatment time relative to the prescribed ultrafiltration settings will be calculated and reported via Table.

The mean and standard deviation of the actual and prescribed UF rate, UF volume, and treatment time will be computed by treatment period across all subjects, where the denominator for the mean calculations will be the total number of treatments in each treatment period for which the subjects contributed non-missing UF data.

Each treatment will be flagged as a success with respect to UF if the actual UF rate is within 10% of the prescribed UF rate. The mean (i.e., success proportion) and standard deviation will be computed by treatment period across all subjects, where the denominator for the mean calculations will be the total number of treatments in each treatment period for which the subjects contributed non-missing UF data.

All analyses of the secondary effectiveness variable will be performed on the ITT population with no missing value imputation and the PP population. The ITT population with no missing value imputation is the primary analysis set.

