5.3 Secondary Outcome Measure

The ultrafiltration (fluid removal) value as reported by the device will be within 10% of the expected fluid removal based on the UF prescription and the Tablo Console fluid removal algorithm.

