8 STUDY PROCEDURES

8.1 Baseline Evaluation

The baseline evaluation will include, but is not limited to, the following testing and assessments, and will be conducted prior to initiating the Run-In period per Appendix B:

- Documentation of consent
- Demographics (Sex, Age, Ethnicity, Race)
- Physical Examination
- Medical History (including history of vascular access)
- Hemodialysis prescription (e.g., equipment, number of times dialyzed per week, and whether inhome or in-clinic settings)
- Laboratory Values
 - Documentation of Laboratory values for 3 months prior to Run-In.
 - Laboratory Testing (hematology and chemistry) as needed*
- Assessment of kinetics
- Routine signs and symptoms
- Concomitant medications

* If the subject has had lab work within two weeks of the run-in period that contains all of the protocol specified tests, a repeat lab draw at baseline is not necessary.

If, after completion and review of the above data, the Subject appears to be a good candidate for study enrollment and is assessed as being able to perform self-care, the Investigator will proceed with the runin period using the Tablo Hemodialysis System.

8.2 1-week Run-in

The 1-week run-in period will include, but is not limited to, the following testing, procedures, and assessment per Appendix B:

- Subject's Dialysis Prescription Settings
- Pre-dialysis vitals, including body weight, temperature, blood pressure, and heart rate (pulse)
- Number of dialysis sessions completed
- Post-Dialysis body weight
- Assessment of Kinetics
- Concomitant Medications
- Assessment of dialysis interval adverse events (if any)
- Final assessment of Subject eligibility

All treatments will be performed using the Tablo[™] Hemodialysis System. Dialysis personnel, trained on the use of the device, will input the dialysis prescription as detailed below:

The dialysis prescription will include:

- Access blood flow (set between 300 and 400 ml/min.)
- Dialysate temperature (between 36 and 39 degrees Celsius adjustable by 0.5 degrees increments)
- Composition of dialysate: potassium (limited to 2 mEq/dL versus 3 mEq/dL), bicarbonate (30 to 40 mEq/L adjustable in 1 mEq/L intervals), sodium concentrations (135-145 mEq/L in 1mEq/liter increments)
- Treatment length in minutes between 160 minutes and 240 minutes
- Blood pressure parameters for ultrafiltration
- Heparin dose and anticoagulation parameters

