11.5 Analysis of Secondary Endpoint

The analysis of the secondary endpoint of ultrafiltration rate (UFR) will be conducted on ITT and PP populations. The UFR will be calculated using the following method:

UF Rate = (Fluid Removal Goal + Rinse Back Volume) / Treatment Duration

Where,

Fluid Removal Goal = Today's Weight – Prescribed Estimated Dry Weight

And,

Rinse Back Volume = The volume of saline, 300mL, returned to the patient at the end of treatment.

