	Renal Failure NOS	xxx (xxx%)
	Glomerulonephritis	xxx (xxx%)
	Polycystic Kidney Disease	xxx (xxx%)
	Other	xxx (xxx%)
Unspecified	xxx (xxx%)	

STATKING Clinical Services (month day, year)
 Source Program: xxxxxxxx.sas

Table 5. Summary of Weekly Standardized Kt/V by Treatment Period
 Outset Medical - Study No. 2014-01
 ITT Population (N=xxx)

Treatment Period	Mean	Std Dev	n	Min	Max	Median
In-Center	xxx	xxx	xxx	xxx	xxx	xxx
In-Home	xxx	xxx	xxx	xxx	xxx	xxx

STATKING Clinical Services (month day, year)
 Source Program: xxxxxxxx.sas

The format of this table will be repeated for the ITT population with missing value imputation and for the PP population.

Table 8. RMANOVA for Weekly Standardized Kt/V - Tests of Fixed Effects
 Outset Medical - Study No. 2014-01
 ITT Population (N=xxx)

Source	Tests of Fixed Effects			
	NDF	DDF	Type III F	Pr > F
Subject	xx	xx	xxx	xxx
Treatment Period	xx	xx	xxx	xxx
Week	xx	xx	xxx	xxx

STATKING Clinical Services (month day, year)
 Source Program: xxxxxxx.sas

The format of this table will be repeated for the ITT population with missing value imputation and for the PP population.

Table 9. RMANOVA for Weekly Standardized Kt/V - LS Means and Standard Errors
 Outset Medical - Study No. 2014-01
 ITT Population (N=xxx)

Treatment Effect	Level	Least Squares Mean (LSMean) and Standard Error (SE)		p-Value ^a
		LSMean	SE	
Treatment Period	In-Center	xxx	xxx	xxx
	In-Home	xxx	xxx	xxx

^a One-sided p-value for test of H0: Mean Weekly Standardized Kt/V ≤ 2.1 vs. H1: Mean Weekly Standardized Kt/V > 2.1.
 STATKING Clinical Services (month day, year)
 Source Program: xxxxxxxx.sas

The format of this table will be repeated for the ITT population with missing value imputation and for the PP population.

Table 14. Summary of Ultrafiltration Rate and Volume Actual vs. Prescribed by Treatment Period
 Outset Medical - Study No. 2014-01
 ITT Population (N=xxx)

Treatment Parameter	In-Center			In-Home		
	Mean	Std Dev	n	Mean	Std Dev	n
Prescribed UF Volume	xxx	xxx	xxx	xxx	xxx	xxx
Prescribed Treatment Time	xxx	xxx	xxx	xxx	xxx	xxx
Prescribed UF Rate	xxx	xxx	xxx	xxx	xxx	xxx
Actual UF Volume	xxx	xxx	xxx	xxx	xxx	xxx
Actual Treatment Time	xxx	xxx	xxx	xxx	xxx	xxx
Actual UF Rate	xxx	xxx	xxx	xxx	xxx	xxx
Success Rate ^a	xxx	xxx	xxx	xxx	xxx	xxx

^a Where success is ultrafiltration rate achieved within 10% of the prescribed rate.
 STATKING Clinical Services (month day, year)
 Source Program: xxxxxxxx.sas

The format of this table will be repeated for the PP population.

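### UF success is scored on rate while Protocol 5.3 defines the outcome as fluid removed, and the two rules can classify shortened or prolonged sessions in opposite ways

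*SAP*

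**What the plan says.** Protocol 5.3 states the outcome as a quantity of fluid: "The ultrafiltration (fluid removal) value as reported by the device will be within 10% of the expected fluid removal". The sentence goes on to base that expectation on the UF prescription and on the console's own removal algorithm, which neither document describes. This outcome, repeated in the synopsis, carries the only 10% tolerance in the protocol.

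SAP 4.2.2 applies the tolerance to a different quantity, and counts a treatment as a success "if the actual UF rate is within 10% of the prescribed UF rate". The Table 14 footnote in SAP Appendix B agrees: "Where success is ultrafiltration rate achieved within 10% of the prescribed rate". The denominator is every treatment with non-missing UF data, with no exclusion for sessions that ended early. SAP 4.1.2 lists UF volume and treatment time as variables in their own right, and Table 14 shows their actual and prescribed means. Neither has a success flag.

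Protocol 11.5 sides with the SAP on the name of the endpoint: "The analysis of the secondary endpoint of ultrafiltration rate (UFR) will be conducted on ITT and PP populations". Its formula is "UF Rate = (Fluid Removal Goal + Rinse Back Volume) / Treatment Duration". Because the numerator is the goal, this yields a prescribed rate only. Section 11.5 sets no tolerance and does not say how an actual rate is derived.

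**The concern.** A rate divides out treatment time. A session can run at the right rate and still fall short of the prescribed volume because it ended early. It can also remove the whole volume at a lower average rate because it ran long. Where session length departs from prescription, a rate flag and a volume flag therefore answer different questions.

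Shortened sessions are foreseen: alarms that end treatment are a recorded observation (Protocol 9.1.3) and are tabulated in SAP Table 34. At stake is whether the proportion reported for the protocol's only secondary outcome measures what Protocol 5.3 says it measures.

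**Working it through.** The documents give no expected proportion, power or sample size for the UF endpoint, so there is no figure to reproduce. The check is direct arithmetic on the two rules.

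**Inputs**
- Tolerance of 10% on fluid removed: Protocol 5.3.
- Tolerance of 10% on rate, per treatment: SAP 4.2.2 and Table 14.
- Prescribed session length: "Treatment length in minutes between 160 minutes and 240 minutes" (Protocol 8.2).
- Rinse back: "The volume of saline, 300mL, returned to the patient at the end of treatment" (Protocol 11.5).
- Assumption A: actual rate = actual volume / actual time. This is the natural reading of Table 14, which lists all three, but it is not stated.
- Assumption B: expected removal is for the full prescribed session.

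**Rules.** Let v = actual/prescribed volume and t = actual/prescribed time.
- Protocol 5.3 passes if 0.90 ≤ v ≤ 1.10.
- SAP 4.2.2 passes if 0.90 ≤ v/t ≤ 1.10.

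**Stopped early at the prescribed rate.** Here v = t, so v/t = 1.00 always. The volume rule fails once t < 0.90.

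**Full volume, prolonged.** Here v = 1.00 and the rate ratio is 1/t. The rate rule fails once t > 1/0.90 = 1.111, an overrun above 11.1%. That is 17.8 min on 160, 22.2 min on 200 and 26.7 min on 240.

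| Prescribed, actual (min) | v | v/t | Volume rule (5.3) | Rate rule (SAP) |
|---|---|---|---|---|
| 240, 216 | 0.90 | 1.00 | pass | pass |
| 240, 180 | 0.75 | 1.00 | fail | pass |
| 240, 120 | 0.50 | 1.00 | fail | pass |
| 240, 252 (+5%) | 1.00 | 0.952 | pass | pass |
| 240, 264 (+10%) | 1.00 | 0.909 | pass | pass |
| 210, 240 (+14.3%) | 1.00 | 0.875 | pass | fail |

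**In mL**, with an assumed goal of 2400 mL: 2400 + 300 = 2700 mL.
- Over 240 min this is 675 mL/h. Stopped at 120 min, 1350 mL is removed, still at 675 mL/h.
- Over 210 min it is 771.4 mL/h. Delivered over 240 min it is 675 mL/h, and 675/771.4 = 0.875.

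The ratios do not depend on the assumed goal.

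**If the assumptions change**
- Without A: if actual rate divides by prescribed time, the rate ratio equals v and the two rules coincide.
- Without B: if expected removal is the prescribed rate times the time delivered, the volume ratio becomes v/t and the early-stop discrepancy disappears.

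**Rinse back.** If actual volume is net and prescribed volume includes the 300 mL, a perfectly delivered 2400 mL goal scores 2400/2700 = 0.889. That is a failure from accounting alone.

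**The case against.** The strongest reply is that the SAP follows the protocol's own analysis section, which names the endpoint as a rate, and that no order of precedence between 5.3 and 11.5 is given. This stands. A reader might infer that the SAP departs from an unambiguous protocol definition, but the documents show a conflict inside the protocol that the SAP resolved one way. The reason to prefer 5.3 is that it alone states the outcome with a criterion.

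A second reply is that 5.3 can be read as device accuracy: removal against what the console should have removed in the time it ran. The reference to the algorithm allows this reading, and under it a session stopped early at the right rate is a genuine success. This also stands until expected removal is defined.

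A third is that under-removal would not be hidden, since Table 14 shows mean actual and prescribed volume and time. That is partly right. However, treatments above and below target can offset each other in a mean, so the means do not replace a per-treatment flag.

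Three stronger inferences are tempting and not supported:
- *Home results are the most distorted.* The documents give no early-termination rate for either setting. Compliance with treatment time is reviewed weekly in both periods (Protocol 8.6).
- *The rate flag inflates success.* Early stops would move from success to failure on volume, and long full-volume sessions the other way. The net direction is unknown.
- *Any prolonged session fails on rate.* At full volume, overruns up to 11.1% pass both rules.

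**Conclusion.** The point holds as an inconsistency between Protocol 5.3 on one side and Protocol 11.5 with SAP 4.2.2 and Table 14 on the other. Under assumptions A and B it changes per-treatment classification in both directions: for sessions run at the prescribed rate but stopped before 90% of prescribed time, and for full-volume sessions that overrun by more than 11.1%. If either assumption fails, the discrepancy shrinks or vanishes, which is why the missing definitions are part of the point.

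Its reach is limited. UF success has no hypothesis or threshold proportion, and plays no part in the success criteria of Protocol 11.3 or in the sample size. How many treatments would change class cannot be derived from the documents. It is worth correcting because this is the protocol's only secondary outcome measure and the correction is cheap.

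**What to change.** - In SAP 4.2.2 and Table 14, flag a treatment as a success when actual UF volume is within 10% of expected UF volume. Include or exclude the 300 mL rinse back on both sides alike.
- Keep the rate-based flag as a supportive line.
- Define actual UF rate, including which time is the divisor. Define expected fluid removal, stating whether it refers to the full prescribed session or to the time delivered.
- Align the wording of Protocol 11.5 with 5.3, so that the endpoint has one name and one criterion.

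The cost is one derived flag, a few short definitions, a footnote and the wording change in 11.5. Actual and prescribed volumes are already planned for Table 14, so no new data are needed. The reported success proportion may move either way.

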4.2.3 Other Analyses

Analyses described in this section will be performed on the ITT population with no missing value imputation.

Clinically Significant Alarms

The number and percentage of treatments with each alarm type (air in venous lines, low systolic BP, high venous pressure, low venous pressure, blood leaks, and alarms ending treatment) will be reported by treatment period.

Summary statistics (mean, sample size, standard deviation, minimum, maximum, and median) on the number of alarms per subject will be provided by treatment period, time point, and treatment number for each alarm type.

Time to Resolve or Clear Alarms

Summary statistics (mean, sample size, standard deviation, minimum, maximum, and median) on the time to resolve/clear alarms will be provided by treatment period. All alarm types will be combined for this analysis. The denominator in the mean calculations will be the number of alarms in the respective treatment period.

Prescription Changes

The number of prescription changes made from initial input during each dialysis treatment will be summarized via summary statistics (mean, sample size, standard deviation, minimum, maximum, and median) for each treatment period and time point. The denominator in the mean calculations will be the number of treatments in the respective treatment period and time point.

The number and percentage of treatments that required a prescription change will be computed for each subject by treatment period. The denominator for all percentages will be the number of treatments completed by each subject in the respective treatment period.

Feel Cold and Hypotensive Events

The number and percentage of subjects with at least one reported feel cold event and at least one reported hypotension event will be computed by treatment period. The denominator for all percentages will be the number of ITT subjects.

5.0 Analysis of Safety

5.1 Description of Safety Variables

All study-emergent AEs occurring during the study sessions will be recorded and classified on the basis of the Medical Dictionary for Regulatory Activities (MedDRA[®]) terminology. Study-emergent AEs are those AEs with an onset on or after the date of first study treatment. All analysis tables of AEs will be relative to study-emergent AEs.

The primary safety analysis variable is the mean number of adverse events (AEs) from the pre-specified list observed during a dialysis interval as follows:

- Serious AE (SAE)
- Allergic Reaction
- Blood Loss

- Hemolytic Reaction
- Infection
- Intra-Dialysis Event
- Vascular Access Complication
- Pyrogenic Reaction

A dialysis interval is defined as the start of one dialysis treatment until the start of the next dialysis treatment. A dialysis interval is further divided as follows:

- *Treatment*: An event that occurs during dialysis treatment onset through completion
- *Interdialytic*: An event that occurs from the end of the subject's treatment to beginning of dialysis treatment set-up of the next treatment
- *Pre-Treatment*: An event that occurs during dialysis treatment set-up until the start of treatment

Any event that occurs during any of these time periods is considered within the same dialysis interval.

The secondary safety analysis variables are defined as follows:

- All other study-emergent AEs
- Clinical labs (Hematology, Chemistry, and Kinetics [Pre/Post BUN])

5.2 Analysis of Safety Variables

The following describes the safety analyses to be performed for the study. Analysis of the primary safety variable will be performed on the ITT population. All other safety analyses will be performed on the safety population.

Pre-specified Adverse Events for Primary Safety Variable

For each treatment period, a 95% confidence interval will be computed on the pre-specified adverse event rate per dialysis interval. This confidence interval will be computed using the Least Square Mean for the respective treatment period from a generalized linear model containing terms for subject, treatment arm and time points (i.e., a repeated measures analysis using GEE) using a Poisson link function and AR(1) covariance structure. If the AE start date/time is missing, the AE will be counted in the interdialytic interval in which it was observed (if available) or will be randomly assigned (during the final data analysis for the study) to one of the interdialytic periods in the treatment period.

Summary statistics (mean, sample size, standard deviation, minimum, maximum, median) will be computed on the number of pre-specified adverse events per dialysis interval for each treatment period. The same summary

statistics will be calculated by treatment period for the rate of pre-specified adverse events per 100 dialysis treatments.

Additional Analyses of Pre-specified Adverse Events

A table will be provided to show the number and percentage of safety population subjects with at least one pre-specified AE by treatment period and overall for each dialysis treatment interval (treatment, interdialytic, pre-treatment).

A summary table will be constructed to display the following with respect to pre-specified AEs:

- Subjects with at least one pre-specified AE
- Maximum severity, per subject
- Highest relationship to device, per subject
- Highest relationship to treatment, per subject
- Subjects with at least one SAE
- Deaths

All Other Study-Emergent Adverse Events

A table will be provided to show the number and percentage of safety population subjects with at least one study-emergent AE by treatment period and overall for each dialysis treatment interval (treatment, interdialytic, pre-treatment). A similar table will also be provided to show the number and percentage of safety population subjects with at least one occurrence of an AE by categorization (pre-specified AEs or all other AEs) by treatment period and overall.

A summary table will be constructed to display the following with respect to all study-emergent AEs:

- Subjects with at least one study-emergent AE
- Maximum severity, per subject
- Highest relationship to device, per subject
- Highest relationship to treatment, per subject
- Subjects with at least one SAE
- Deaths

Laboratory Tests

Clinical laboratory tests will be performed at Baseline and at approximately every four weeks through study completion (with the exception of pre and post BUN, which are captured weekly). For each quantitative laboratory test, summary statistics (mean, standard deviation, median, range, n) on the raw data as well as changes from baseline will be presented by timepoint. If multiple labs were performed at a given timepoint, the lab results from the date the site is basing clinical care from will be used and summarized in the analysis tables. A summary table will be provided to show the results for all lab tests, and additional tables

will be provided to show the results for a subset of the lab tests as well as to show results for selected individual lab tests, as listed in Section 7.0.

A summary table of abnormal lab results will also be provided. All summary statistics (mean, standard deviation, median, range, n) will be computed relative to the lab results that fell outside of specified ranges on the raw data. These ranges will be determined prior to data analysis.

Pre and post BUN summary statistics will be provided in a separate table to show the results by treatment period, time point, and treatment number. Parameters include pre BUN, post BUN, difference in pre and post BUN, and URR, where URR is defined as (pre BUN minus post BUN) divided by (pre BUN).

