11.3 Analysis of Primary Endpoint

The study is based on the primary endpoints for effectiveness and interval estimates of the safety of the device. The study will be considered a success from a statistical standpoint if:

- 1. Both primary analysis variables pass their respective hypotheses, i.e., H_{a0} and H_{b0} below are rejected in favor of H_{a1} and H_{b1}, respectively,
- 2. The rate of pre-specified adverse events per dialysis interval is estimated to be within the specified error of estimation for each treatment period.

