11.6 Analysis of Adverse Events

All study-emergent AEs occurring during the study sessions will be recorded and classified on the basis of MedDRA terminology for the ITT population. Study-emergent AEs are those AEs with an onset on or after the date of first study treatment. All study-emergent AEs will be categorized by study period (In-Center or In-Home), the number of Subjects reporting study-emergent AEs, severity, device relationship, and seriousness. Serious adverse events (SAEs) will be listed by Subject. SAEs will be categorized by study period, severity, and device relationship. Each Subject will be counted only once within a category using the event with the greatest device relationship and greatest severity.

For each treatment period, a 95% confidence interval will be computed on the pre-specified adverse event rate per dialysis interval. This confidence interval will be computed using the Least Square Mean for the respective treatment period from a generalized linear model containing terms for Subject, arm and time points (i.e., a repeated measures analysis using GEE) using a Poisson link function and AR(1) covariance structure.

Summary statistics (mean, sample size, standard deviation, minimum, maximum, median) will be computed on the number of pre-specified adverse events per dialysis interval for each treatment period. The same summary statistics will be calculated by treatment period for the rate of pre-specified adverse events per 100 dialysis treatments.

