11.8 Sample Size Analysis

The estimated sample size for the trial was based on the safety endpoint and yields an estimate of the rate of pre-specified adverse events per 100 dialysis treatments in each treatment period (In-Center and In-Home use), to a margin of error of less than 1 event per 100 treatments. With a two-sided α =0.05, in order to construct a 95% confidence interval on the rate of pre-specified adverse events per 100 dialysis treatments with half-width less than 1 event per 100 treatments, the sample size required would be n=30 Subjects with 4 dialysis intervals per week for a minimum of 8 weeks (i.e., 30 subjects with a minimum of 32 treatments). The sample size calculation was based on an asymptotic normal theory one sample test using variance estimates that included covariance terms for repeated measurements (4 dialysis intervals per week for 8 weeks) on each Subject with a block diagonal first order autoregressive (AR(1)) covariance structure. This sample size calculation assumed a standard deviation of 0.8 AEs per dialysis interval and a within Subject correlation of pre-specified AE counts of ρ =.50.

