4.2 Analysis of Effectiveness Variables

4.2.1 Analysis of Primary Effectiveness Variable

The weekly standardized Kt/V values will be computed for each subject for the In-Center period and for the In-Home period. The following hypotheses will be tested at a one-sided $\alpha=0.025$ level of significance:

$$H_{a0}: \mu_{IC} \leq 2.1 \text{ vs. } H_{a1}: \mu_{IC} > 2.1$$

and

$$H_{b0}: \mu_{IH} \leq 2.1 \text{ vs. } H_{b1}: \mu_{IH} > 2.1$$

where μ_{IC} is the treatment period mean weekly standardized Kt/V value for the In-Center arm and μ_{IH} is the treatment period mean weekly standardized Kt/V value for the In-Home arm. These hypotheses will be tested using the Least

Square Mean for the respective treatment period from a repeated measures analysis of variance (RMANOVA) containing terms for subject, treatment arm (i.e., In-Center treatment period and In-Home treatment period), and time points (weeks) and using an AR(1) covariance structure.

Summary statistics (mean, sample size, standard deviation, minimum, maximum, and median) will be computed on the weekly standardized Kt/V values for each treatment period.

All analyses of the primary effectiveness variable will be performed on the ITT population with no missing value imputation, the ITT population with missing value imputation, and the PP population. The ITT population with no missing value imputation is the primary analysis set.

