Table 16. Summary of Pre-Specified Adverse Events for Primary Safety Endpoint by Treatment Period
 Outset Medical - Study No. 2014-01
 ITT Population (N=xxx)

	Treatment Period	Mean	95% Confidence Interval	Std Dev	n	Min	Max	Median
Number of Pre-Specified Adverse Events Per Dialysis Interval	In-Center	xxx	(xxx, xxx)	xxx	xxx	xxx	xxx	xxx
	In-Home	xxx	(xxx, xxx)	xxx	xxx	xxx	xxx	xxx
Number of Pre-Specified Adverse Events Per 100 Dialysis Treatments	In-Center	xxx	(xxx, xxx)	xxx	xxx	xxx	xxx	xxx
	In-Home	xxx	(xxx, xxx)	xxx	xxx	xxx	xxx	xxx

STATKING Clinical Services (month day, year)
 Source Program: xxxxxxxx.sas

Table 17. Pre-Specified Study-Emergent Adverse Events Summary for Each Treatment Interval by Treatment Period and Overall
 Outset Medical - Study No. 2014-01
 Safety Population (N=xxx)

Treatment Interval	Treatment Period ^a		
	In-Center	In-Home	Overall
Pre-Treatment	xxx (xxx%)	xxx (xxx%)	xxx (xxx%)
Treatment	xxx (xxx%)	xxx (xxx%)	xxx (xxx%)
Interdialytic	xxx (xxx%)	xxx (xxx%)	xxx (xxx%)

^a Counts represent number of subjects with at least one pre-specified study-emergent adverse event with a start date/time in the respective treatment interval and treatment period. The denominator for all percentages is the number of subjects in the safety population.

STATKING Clinical Services (month day, year)
 Source Program: xxxxxxxx.sas

Table 18. Number and Percent of Subjects with Study-Emergent Adverse Events by Treatment Period and Severity, Relationship to Device, Seriousness, and Overall
 Outset Medical - Study No. 2014-01
 Safety Population (N=xxxx)

	Treatment Period ^a		
	In-Center	In-Home	Overall
Subjects with ≥ 1 Adverse Event (AE)	xxxx (xxxx%)	xxxx (xxxx%)	xxxx (xxxx%)
Maximum AE Severity			
Mild	xxxx (xxxx%)	xxxx (xxxx%)	xxxx (xxxx%)
Moderate	xxxx (xxxx%)	xxxx (xxxx%)	xxxx (xxxx%)
Severe	xxxx (xxxx%)	xxxx (xxxx%)	xxxx (xxxx%)
Highest Relationship of AE to Device			
Not Related [n(%)]	xxxx (xxxx%)	xxxx (xxxx%)	xxxx (xxxx%)
Related [n(%)]	xxxx (xxxx%)	xxxx (xxxx%)	xxxx (xxxx%)
Unknown [n(%)]	xxxx (xxxx%)	xxxx (xxxx%)	xxxx (xxxx%)
Highest Relationship of AE to Treatment			
None [n(%)]	xxxx (xxxx%)	xxxx (xxxx%)	xxxx (xxxx%)
Unlikely [n(%)]	xxxx (xxxx%)	xxxx (xxxx%)	xxxx (xxxx%)
Possible [n(%)]	xxxx (xxxx%)	xxxx (xxxx%)	xxxx (xxxx%)
Probable [n(%)]	xxxx (xxxx%)	xxxx (xxxx%)	xxxx (xxxx%)
Definitely [n(%)]	xxxx (xxxx%)	xxxx (xxxx%)	xxxx (xxxx%)
Subjects Experiencing ≥ 1 Serious AE (SAE)	xxxx (xxxx%)	xxxx (xxxx%)	xxxx (xxxx%)

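### As worded, the Poisson GEE for the primary safety interval has subject and time-point terms in the mean model; with a log link its LS mean collapses or its robust 95% CI under-covers, and subject should be the cluster only, with treatment period the only regressor

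*SAP*

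**What the plan says.** SAP 5.2 bases the primary safety interval on the period LS mean of a "generalized linear model containing terms for subject, treatment arm and time points (i.e., a repeated measures analysis using GEE", with what it calls a Poisson link function and an AR(1) structure. Protocol 11.6 specifies the same: "generalized linear model containing terms for Subject, arm and time points (i.e., a repeated measures analysis using GEE".

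The Kt/V model in SAP 4.2.1 uses a parallel list, "containing terms for subject, treatment arm (i.e., In-Center treatment period and In-Home treatment period), and time points (weeks". Its Appendix B shell, Table 8, is titled "RMANOVA for Weekly Standardized Kt/V - Tests of Fixed Effects" and has a row for Subject. The safety model has no such shell. Table 16 prints the observed mean beside the CI for "Number of Pre-Specified Adverse Events Per Dialysis Interval".

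Success item 2 in Protocol 11.3 requires that the adverse event rate "is estimated to be within the specified error of estimation for each treatment period". The only error figure in the documents is in Protocol 11.8, repeated in SAP 1.3: a CI "with half-width less than 1 event per 100 treatments". That calculation assumes an SD of 0.8 per interval and "a within Subject correlation of pre-specified AE counts of" 0.50.

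Neither document names the link more exactly, says whether the SE is robust or model-based, defines time points for the safety model, or gives an expected event rate.

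**The concern.** In a log-link Poisson model, a factor level with no events has no finite coefficient. Thirty subject levels with sparse counts make such a level likely, and an LS mean that averages coefficients on the log scale inherits the problem. Even without an empty level, subject terms absorb the between-subject variation that a subject-clustered sandwich SE is meant to measure, and averaging logs pulls the LS mean below the arithmetic rate.

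At stake is the primary safety result itself. If item 2 is judged on the half-width of 1 per 100, a falsely narrow interval could appear to satisfy a trial success criterion.

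**Working it through.** **Inputs.** From the documents: 30 subjects, 2 periods, 32 intervals per period, correlation 0.50, SD 0.8, target half-width 0.01 per interval. Assumed: the event rate r (a range is shown), a log link, robust SEs, and time points taken as weeks 1 to 8 shared by both periods.

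**The plan's own figure.** The AR(1) variance inflation over 32 intervals is 1 + 2Σ(1 − k/32)0.5^k = 2.875. The half-width is 1.96 × 0.8 × √(2.875/(32 × 30)) = 0.0858, or 8.58 per 100, not below 1. This is a separate problem, and the argument below does not rest on it. If counts are Poisson instead, a half-width below 0.01 is attainable up to r = 960 × (0.01/1.96)² = 0.0250 with independent counts, and 0.0250/2.875 = 0.0087 with correlation 0.50.

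**(a) Subjects with no events.** Over 64 intervals, P0 = exp(−64r) for independent counts. With a Poisson autoregression at 0.50 restarting each period, P0 = exp(−2r(1 + 0.5 × 31)) = exp(−33r). The chance of at least one such subject is 1 − (1 − P0)^30:

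| Rate per 100 | Independent | Correlation 0.50 |
|---|---|---|
| 2.5 | 99.9% | over 99.99% |
| 5 | 71% | 99.8% |
| 10 | 5% | 68% |
| 20 | under 0.1% | 4% |

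That subject's coefficient falls by about 1 per iteration, so with k such subjects each iteration multiplies the LS mean by about exp(−k/30). In one data set with a single such subject and a raw In-Center rate of 9.6 per 100, the LS mean read 6.0, 4.3 and 3.3 per 100 at iterations 10, 20 and 30. The robust SE stayed near 0.08 on the log scale, while the model-based SE rose from 4 to 33,000.

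**(b) Every subject has events.** The fit converges. Under working independence each subject's residuals sum to zero, so the sandwich SE misses variation in subject totals. Simulation used an intercept with 29 subject, 1 period and 7 week dummies, equal weights on the log scale, and 500 converged trials per rate with independent counts:

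| Rate per 100 | Coverage, subject as regressor | Coverage, period only, subject as cluster | LS mean vs observed | Robust SE / actual SD |
|---|---|---|---|---|
| 5 | 66% | 93% | 16% lower | 0.70 |
| 10 | 64% | 94% | 10% lower | 0.65 |

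Repeat runs put coverage at about 60 to 66%. With an estimated AR(1) working correlation it was 65% at 5 and between 56% and 61% at 10. With counts generated at correlation 0.50 it was 57% against 92% at 10, and 59% against 95% at 20. At 64 per 100, where a Poisson SD equals 0.8, it was 80% against 93%.

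Both half-widths were below 1 per 100 in 81% of converged trials at 5 per 100, against 0% for the period-only model. One converged example: observed 5.10 per 100, CI with subject as regressor 3.57 to 4.78, period-only CI 4.12 to 6.33.

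**(c) Event-free time points, subject as cluster only.** Each week level holds 30 × 2 × 4 = 240 intervals. The chance of at least one empty week is 1 − (1 − exp(−240r))^8:

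| Rate per 100 | Empty week | Coverage, week terms kept | Coverage, period only |
|---|---|---|---|
| 0.87 | 65% | about 35% | about 94% |
| 1.0 | 53% | about 44% | about 94% |
| 1.5 | 20% | about 77% | about 94% |

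These coverages depend on the stopping iteration. At 2.5 to 10 per 100, week terms did little harm (coverage 92 to 95%). If time points are the 32 individual intervals, each level holds 60, and at 5 per 100 the chance of an empty level is 1 − (1 − exp(−3))^32 = 80%.

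**The case against.** The best defence is that the parenthesis explains the term list: a GEE needs a clustering unit, the sentence names subject nowhere else, and so subject may mean only the cluster. Table 8 belongs to a different, Gaussian model. This stands as far as it goes: the text allows that reading but does not state it, and it lists subject alongside arm and time points. Nor would that reading suffice, because (c) applies to it.

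A reader might infer that the plan definitely fits subject as a fixed effect, so that the safety interval is bound to be wrong. The documents do not support that. A reader might equally infer that making subject the cluster removes the problem; at low rates with time terms kept, it does not.

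Two further points have weight. A collapsed fit would not converge and would look odd beside the observed mean in Table 16. In converged fits, however, the CI still contained the observed mean in 67% of periods at 5 per 100 and 85% at 10, so the error would often go unnoticed. Those fits need every subject to have an event, which happens in 29% of trials at 5 per 100 with independent counts and 0.2% with correlation 0.50. Model-based SEs under-cover less (78 to 93% in homogeneous subjects) but diverge when a subject has no events.

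**Conclusion.** The specification should be fixed. Followed as written, it gives an invalid primary safety CI over the range of rates examined: an LS mean that depends on when iteration stops where a subject has no events, and roughly 60 to 66% coverage at 5 to 10 per 100 where none does. A half-width below 1 is validly attainable only up to about 2.5 per 100 (0.87 with correlation 0.50), where a zero-event subject is near certain.

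This rests on four inferences (subject as regressor, log link, robust SE, weeks as time points) and on assumed event rates. Confidence is therefore medium. The effect on trial success is conditional too: Protocol 11.3 does not say that its error of estimation is the half-width in Protocol 11.8, so a false declaration of success is possible but not established.

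**What to change.** In SAP 5.2 and Protocol 11.6, state for the primary safety CI:

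- Poisson distribution with log link;
- subject only as the GEE clustering unit, not in the mean model;
- treatment period as the only regressor, with the time-point terms dropped (the variant checked here), or predicted rates averaged on the response scale;
- AR(1) working correlation retained;
- robust standard errors.

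Optional additions are a small-sample SE correction for 30 clusters and an exact Poisson interval for a period with no events (0 events in 960 intervals gives an upper limit of −ln(0.025)/960 = 0.0038, or 0.38 per 100).

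The cost is wording only, with no new data. Week-by-week adjustment of the primary safety CI is given up if the time terms are dropped.
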